6.2.1 Sensitivity Analyses of Key Secondary Efficacy Endpoints

A sensitivity analysis will be performed using the CMH testing described in Section 6.1, including only the subset of subjects who had the opportunity to complete 52 weeks of treatment in the SHP647-303 study prior to the implementation of Protocol Amendment 3 at their site.

Additionally, the key secondary endpoints will be summarized separately for the Placebo Responder FAS by treatment group without inferential methods.

In addition, if significant noncompliance with regulatory requirements during the course of the study is detected or reported at any clinical site, additional sensitivity analyses may be conducted on the key secondary endpoints using the same approach but excluding all subjects from the noncompliant site(s).

6.2.2 Supplementary Analyses of Key Secondary Efficacy Endpoints

No supplementary analyses of the key secondary efficacy endpoints are planned for this study.

6.3 Analyses of Other Secondary Efficacy Endpoints

Other secondary endpoints will be summarized by descriptive statistics at each visit the endpoint is assessed and presented by treatment group for the Ontamalimab Responder FAS. The other secondary endpoints will be analyzed using the same approach as described for the primary endpoint. Subjects with missing other secondary endpoint data at the Week 52 visit will be considered failures and counted as nonresponders. These endpoints also will be summarized for the Placebo Responder FAS by treatment group without inferential methods.

The other secondary endpoints and analyses are noted below.

- Remission, defined as a total Mayo score ≤ 2 with no individual subscore (SF, RB, endoscopy [modified, excludes friability], and physician's global assessment) exceeding 1, at Week 52. A CMH chi-square test that is described in Section 6.3 will be used to compare the proportion of subjects with remission

for each active treatment group to placebo group (25 mg in induction placebo group or 75 mg in induction placebo group; placebo groups are not pooled) at Week 52.

- Clinical remission over time with both RB and SF subscores of 0. A CMH chi-square test that is described in Section 6.3 will be used to compare the proportion of subjects with clinical remission for each active treatment group to placebo group (25 mg in induction placebo group or 75 mg in induction placebo group; placebo groups are not pooled) over time.
- Sustained endoscopic remission, ie, in endoscopic remission at the SHP647-303 Week 52 visit among subjects who were in remission at the time of MNT baseline, as defined by a centrally read endoscopic subscore of 0 or 1 (modified, excludes friability). A CMH chi-square test that is described in Section 6.3 will be used to compare the proportion of subjects with sustained endoscopic remission for each active treatment group to placebo group (25 mg in induction placebo group or 75 mg in induction placebo group; placebo groups are not pooled) at Week 52.

6.3.1 Sensitivity Analyses of Other Secondary Efficacy Endpoints

No sensitivity analyses of other secondary efficacy endpoints are planned for this study.

[figure not shown]
6.3.2 Supplementary Analyses of Other Secondary Efficacy Endpoints

No supplementary analyses of other secondary efficacy endpoints are planned for this study.

6.4 Multiplicity Adjustment

The global FWER for the statistical tests of the primary and key secondary endpoints will be strongly controlled at .05 (2-sided). To control the FWER, graphical methods discussed in [Bretz et al. \(2009\)](#) will be utilized to propagate α from primary to key secondary endpoints and between the 2 ontamalimab treatment groups and placebo comparisons. Alpha is initially split equally at the .025 level (2-sided) for each of the pairwise treatment comparisons for the primary endpoint (P) and alpha is propagated in a hierarchical manner to each of the 7 key secondary endpoints (K1-K7) within a pairwise treatment comparison. A graphical visualization of the α propagation is presented in [Figure 3](#).

Figure 3: Visualization of Alpha Propagation

Only p-values that are significant according to this graphical approach are inferential and statistically significant. All other p-values are descriptive.

6.5 Subgroup Analyses

No subgroup analyses are planned for this study.

7. SAFETY ANALYSIS

The safety analyses will be performed using the Safety Set. Safety variables include adverse events (AEs), clinical laboratory variables, vital signs, electrocardiogram (ECG) variables, anti-drug antibody (ADA) and neutralizing antibody (NAb) variables, and neurological variables. For each safety variable, the last value collected prior to the first dose of double-blind IP in induction study (SHP647-301 or SHP647-302) will be used as baseline for all analyses of that safety variable. A final on-treatment assessment will be defined as the last valid assessment obtained after MNT baseline and through the end of treatment visit.

Safety outputs will be presented by treatment group listed in Appendix 16.6. The primary set will present data by SHP647-303 treatment, regardless of the treatment in the induction study. The secondary set will present data by both the induction study treatment and the SHP647-303 study treatment.

7.1 Adverse Events

Adverse events will be coded using MedDRA Version 19.1 2016.

Treatment-emergent AEs (TEAEs) are defined as AEs with start dates at the time of or following the first exposure to IP in the SHP647-303 study.

An overall summary of the number of subjects with TEAEs will be presented, including the number and percentage of subjects with any TEAEs, serious TEAEs, TEAEs related to IP, related serious AEs (SAEs), TEAEs leading to discontinuation of IP, TEAEs leading to study discontinuation, and TEAEs leading to death.

The number of events, incidence, and percentage of subjects reporting TEAEs will be presented by treatment group as listed in Appendix 16.6; by preferred term; by SOC and preferred term; and by SOC, preferred term, and maximum severity. Treatment-emergent AEs considered related to IP will also be summarized by SOC and preferred term. If more than one AE occurs with the same preferred term for the same subject, then the

subject will be counted only once for that preferred term using the most severe and most related occurrence for the summarization by severity and by relationship to IP.

The most common TEAEs (incidence $\geq 2\%$ in any treatment group) will be summarized by preferred term in descending frequency by treatment group as listed in Appendix 16.6.

Serious TEAEs, TEAEs leading to discontinuation of the study or study medication, and injection site AEs will be summarized by SOC, preferred term, and treatment group as defined in Appendix 16.6. Adverse events leading to withdrawal, serious AEs, and deaths will be similarly summarized or listed.

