### 5.2.3 Rescue Therapy

Subjects must maintain their stable dose of background UC treatment, unless dose reduction or discontinuation are required due to associated AEs. If a subject requires initiation of a new therapy or increase in glucocorticoids for UC above the SHP647-303 baseline level, the subject should be withdrawn from study treatment and enter the safety follow-up period, and appropriate treatment should be given at the discretion of the investigator.

Subjects who enter the follow-up period will no longer need to abstain from the medications that were prohibited during the baseline and treatment periods. High-dose glucocorticoids and other UC treatments will be allowed. Biologics or nonbiologic immunosuppressants should not be initiated during the safety follow-up period without prior discussion with the sponsor study physician or designee due to the long half-life of ontamalimab.

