#### **6.2.4 Unblinding the Treatment Assignment**

Whenever possible, the investigator or subinvestigator should contact the Shire physician and/or assigned medical monitor before breaking the blind. It is understood that in an emergency situation it may not be possible to communicate with the study team before breaking the blind. The safety of the subject should be of primary concern. When the blinding code is broken the reasons must be fully documented.

In the event that the treatment assignment is broken, the date, the signature of the person who broke the code, and the reason for breaking the code are recorded on the IRT and the source documents. Upon breaking the blind, the subject is withdrawn from the study, but should be followed up for safety purposes. The IRT will notify the relevant personnel in the event of any code break. Code-break information is held by the pharmacist/designated person at the site.

Due to early termination of the ontamalimab program, the sponsor is providing an option for subjects who are responding to active treatment in this maintenance study or who are on placebo and had responded to active treatment in an induction study to continue to receive ontamalimab in the long-term safety extension study SHP647-304. As this eligibility criterion into SHP647-304 depends on the blinded treatment assignment in this study, for these subjects, there is a potential for the treatment assignment in this study to be unblinded at the ET visit when assessing whether a subject can be a rollover into the SHP647-304 study or proceed to the safety follow-up period. The date of the ET visit will be recorded.

In addition, due to the early discontinuation of the SHP647 program, the SHP647-304 study is planned to be unblinded prior to the database lock in this study, which would unblind the treatment assignment in this study for a significant portion of subjects. As such, this study will be considered unblinded when the SHP647-304 study is unblinded, and the date of study unblinding will be recorded.

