### 7.2.3 Follow-up Period: Visit 15 (Week 64)

Subjects who are withdrawn early from the study, or who do not enter the LTS study (SHP647-304), should enter the 12-week safety follow-up period for safety monitoring. Subjects who are proceeding to the LTS study (SHP647-304) will not enter the safety follow-up period.

For subjects who complete SHP647-303, safety follow-up will occur 12 weeks following the subject's last visit (Week 52) in the treatment period.

At the end of the 12-week safety follow-up period, there will be a visit at the site on Day 448  $\pm$ 10 days (for subjects who completed the 52-week treatment period) or 12 weeks  $\pm$ 10 days after the ET visit (for subjects who are withdrawn early from the study), which will form the Week 64 visit (Visit 15). The final 12-week safety follow-up visit is preferred to be on-site; however, due to a pandemic (eg, coronavirus disease [COVID-19]) or other future similar unexpected public health concerns requiring physical distancing that may result in subjects missing their visits, the visit may also be done at a subject's home provided a qualified site staff member performs the evaluations following DTP guidance. The assessments and procedures specified in [Table 1](#) will be performed, including querying for SAEs, AEs, and concomitant medications and procedures. All AEs and SAEs that are not resolved at the time of this visit will be followed to closure (see [Section 8.1](#)).

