### 7.3.3.4 Adverse Event Collection

At each study visit, subjects will be questioned in a general way to ascertain if AEs have occurred since the previous visit (eg, “Have you had any health problems since your last visit?”). Adverse events are collected from the time informed consent and/or assent is signed until the end of the defined safety follow-up period stated in Section 7.2.3 (See Section 8, Adverse and Serious Adverse Events Assessment).

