## 9.9 Safety Analyses

All safety analyses will be performed using the safety set. Subjects will be analyzed according to the treatment they actually received.

Adverse events will be coded using the Medical Dictionary for Regulatory Activities.

Treatment-emergent AEs are defined as AEs with start dates at the time of or following the first exposure to investigational product in the SHP647-303 study. The number of events, incidence, and percentage of TEAEs will be calculated overall, by SOC, by preferred term, and by treatment group. Treatment-emergent AEs will be further summarized by severity and relationship to investigational product. Adverse events leading to withdrawal, SAEs, and deaths will be similarly summarized or listed. Adverse events of special interest will be summarized by treatment group.

Clinical laboratory tests, vital signs, and ECG findings will be summarized by treatment group and visit. Potentially clinically important findings will also be summarized or listed.

Antidrug antibody data will be summarized by treatment group and visit.

Further details of safety analyses will be described in the SAP.

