7.2 Clinical Laboratory Data

Descriptive statistics for clinical laboratory values (in conventional units) and changes from induction study (SHP647-301 or SHP647-302) baseline at each assessment time point for quantitative variables will be presented by treatment group as listed in Appendix 16.6 for the following clinical laboratory variables. The number and percentage of subjects for qualitative variables in urinalysis will be presented by treatment group as listed in Appendix 16.6 in the Safety Set.

Serum chemistry

- alkaline phosphatase
- aspartate aminotransferase (AST)
- alanine aminotransferase (ALT)
- total bilirubin
- total protein
- albumin
- glucose
- blood urea nitrogen
- creatinine
- sodium
- potassium
- chloride
- calcium
- carbon dioxide

Hematology

- hemoglobin
- hematocrit
- mean corpuscular hemoglobin
- mean corpuscular hemoglobin concentration
- mean corpuscular volume
- erythrocyte (red blood cell) count
- leukocyte (white blood cell) count
- neutrophils
- lymphocytes
- monocytes
- eosinophils
- basophils
- platelet count

Urinalysis

- glucose
- protein
- specific gravity
- pH
- nitrite
- bilirubin
- ketones
- hemoglobin
- urobilinogen
- leukocyte esterase

Clinical laboratory test values are potentially clinically important (PCI) if they meet either the low or high PCI criteria listed in Table 3. The number and percentage of subjects with post-MNT baseline (value collected after the first exposure to IP in the SHP647-303 study) PCI values will be tabulated by treatment group as listed in Appendix 16.6. The percentages will be calculated relative to the number of subjects with at least 1 post-MNT baseline assessment. The numerator is the total number of subjects with at least 1 post-MNT baseline PCI value. A supportive listing of subjects with post-MNT baseline PCI values will be provided including the subject number, site, induction study (SHP647-301 or SHP647-302) baseline, MNT baseline, and post-MNT baseline values.

Figures will be presented for hematology and chemistry to show the changes in laboratory parameters over time. Data will be presented as box-and-whisker plots by treatment group as listed in Appendix 16.6 at each visit, with 1 laboratory parameter per page.

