12.5 Repeated or Unscheduled Assessments of Safety Parameters

Assessments will be assigned to visits based on the date the assessment took place regardless of the completed CRF page. Assessments will be mapped to visits as outlined in [Table 6](#) to Table 9.

If a subject has more than 1 assessment mapped into a given study visit with non-missing results, the assessment closest to the planned visit will be used for analysis. However, all post-MNT baseline assessments will be used for PCI value determination.

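### The TEAE and laboratory/vital-sign PCI windows have no stated end, and under Amendment 3 the proportion of subjects observed through the 12-week follow-up can differ by arm

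*SAP*

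**What the plan says.** **Adverse events.** SAP 7.1 counts as treatment-emergent those events "defined as AEs with start dates at the time of or following the first exposure to IP in the SHP647-303 study". Protocol 9.9 agrees: "Treatment-emergent AEs are defined as AEs with start dates at the time of or following the first exposure to investigational product". Neither gives an upper limit. Under Protocol 7.3.3.4, events are collected "until the end of the defined safety follow-up period stated in Section 7.2.3". Protocol 7.2.3 adds: "Subjects who are proceeding to the LTS study (SHP647-304) will not enter the safety follow-up period". The window thus closes at Week 52/ET for a rollover subject and up to 12 weeks later for a followed subject.

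**PCI values.** SAP 7.2 counts any laboratory "value collected after the first exposure to IP in the SHP647-303 study", SAP 7.4 counts post-MNT baseline vital signs, and SAP 12.5 says that "all post-MNT baseline assessments will be used for PCI value determination". SAP Tables 6 and 9 give vital signs, weight and safety laboratory tests a follow-up window after EOT. SAP Table 8 gives ECG none.

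**Route out of the study.** Protocol 6.2.4 sets this condition for offering SHP647-304: "responding to active treatment in this maintenance study or who are on placebo and had responded to active treatment in an induction study". It says that this criterion depends on the blinded assignment. Induction response was an entry criterion for everyone (Protocol 4.1). The Amendment 3 rationale states that subjects given placebo in both studies cannot roll over.

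**Display.** SAP 7 presents safety mainly by maintenance treatment with induction groups pooled, and secondarily by induction/maintenance combination (SAP 16.6). Subject-years are computed (SAP 5.6), but no exposure-adjusted event rate and no on-treatment event table is planned.

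**The concern.** On the 6.2.4 wording, an ontamalimab subject who is not responding at early termination goes to follow-up. An active-induction placebo subject in the same state may still roll over, because only the induction response is needed. Among placebo-induction subjects the direction reverses: placebo/placebo subjects all go to follow-up, while ontamalimab responders may leave.

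The extra time is not neutral. It comes disproportionately from current non-responders, and Protocol 5.2.3 relaxes the treatment rules: "Subjects who enter the follow-up period will no longer need to abstain from the medications that were prohibited" (the same section asks for discussion with the sponsor before biologics or nonbiologic immunosuppressants are started). Significant worsening of colitis is recorded as an adverse event (Protocol 8.1.5), and CD and UC were the most common serious events across earlier studies (Protocol 1.3). An apparent ontamalimab excess in TEAE, SAE, AESI or PCI percentages could arise partly from longer observation and not from the drug.

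**Working it through.** **The plan's timeline.** 52 + 12 = 64 weeks, and Day 364 + 84 = Day 448. Both agree with Protocol 3.2 and 7.2.3. Follow-up is therefore 12/64 = 18.8% of a completer's window, or 12/36 = 33.3% if treatment closes at Week 24.

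**Inputs**
- *T*: weeks on study before the Week 52/ET visit; 52 or 24 (24 is illustrative).
- *p*: event risk over those *T* weeks, the same in both arms; 10% or 60% (assumed).
- *f*: share of affected ontamalimab subjects entering follow-up; 50%. This borrows the 50% Week 52 composite-response premise in Protocol Table 8 and assumes that every eligible subject rolls over.
- Placebo share entering follow-up: 0.
- *g*: share of the column leaving under Amendment 3. The documents do not give it; *g* = 1 is the ceiling.

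**Formula.** With constant hazard h = −ln(1 − p)/T, followed subjects have risk 1 − exp(−h(T + 12)). The excess in the ontamalimab column is

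g × f × (1 − p) × [1 − (1 − p)^(12/T)].

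**Results at g = 1, f = 0.5**

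| p | T = 52 | T = 24 |
|---|---|---|
| 10% | 0.5 × 0.9 × (1 − 0.9^(12/52)) = 1.08 points, giving 11.1% | 0.5 × 0.9 × (1 − 0.9^0.5) = 2.31 points, giving 12.3% |
| 60% | 0.5 × 0.4 × (1 − 0.4^(12/52)) = 3.81 points, giving 63.8% | 0.5 × 0.4 × (1 − 0.4^0.5) = 7.35 points, giving 67.4% |

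**Range.** Halving either *f* or *g* halves the excess: the 10% event then gains 0.54 or 1.15 points. If the hazard doubles during follow-up (assumed), the 10% event becomes 12.1% or 14.5%. With equal follow-up shares in the two arms the artefact is zero, as it is if the window closes at EOT for everyone.

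**Pooled display.** Planned placebo/placebo subjects number 104/5 = 20.8 of 148 + 148 + 20.8 = 316.8 placebo subjects, or 6.6%. If all of them are followed, the excess for a 10% event at 52 weeks falls from 1.08 to 0.94 points, so the offset is small.

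**In subjects.** A planned ontamalimab column is 148 + 41.6 = 189.6. Scaled by 366/696 (assuming the planned mix), that is about 100, so 1.08 to 2.31 points is one to two subjects at g = 1.

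**The case against.** **The rollover rule is not uniform.** The Protocol synopsis and 3.1 speak of subjects who benefited from active treatment in either study. SAP 3.3 is similar. Protocol 3.1.3 offers the extension to treatment failures with no condition on arm, and Table 1 footnote d and Protocol 7.2.2.2 still schedule for that. Every active-induction subject responded in induction, so the broader wording would shrink or remove the contrast among them. The governing criteria are in SHP647-304 Amendment 4, which is not among the documents. This stands. It does not remove the placebo/placebo difference, since the Amendment 3 rationale excludes those subjects expressly.

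**A stronger inference is tempting but unsupported.** A reader might infer that events are counted in one arm and not collected in the other. They are not so divided: every group except placebo/placebo can contain both rollover and followed subjects, so any bias is a difference in proportions. Collection also stops at the end of follow-up, even though the TEAE definition has no end. Nor is follow-up simply drug-free time. With the 16-day half-life cited in the Amendment 3 summary, 2^(−28/16) = 30% of drug remains 28 days after the last dose and 2^(−56/16) = 9% after 56 days. ECG cannot be included, because it has no follow-up window.

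**The size is an upper-end figure.** The 50% premise is for Week 52 with missing data counted as failure, so it probably overstates non-response among subjects still on treatment. Constant-hazard arithmetic also does not describe PCI counts, where follow-up has one scheduled visit.

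**Partial safeguards exist.** Disposition by group reports rollover and follow-up entry (SAP 5.1), the secondary display isolates placebo/placebo, and no formal safety testing is planned (Protocol 9.5). These make the imbalance visible but do not correct the percentages.

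**Conclusion.** The point holds as a difference in observation windows. The TEAE and laboratory/vital-sign PCI rules have no common end, follow-up data enter those tables, and Protocol 6.2.4 makes the route for Amendment 3 leavers depend on the assigned arm. No planned table corrects for it.

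The likely direction, on the 6.2.4 wording, is towards ontamalimab among active-induction subjects and towards placebo/placebo among placebo-induction subjects. The first depends on how the rollover passages are reconciled; the second does not. The size is modest: about 1 to 2 points on a 10% event under assumptions chosen at the upper end, scaling down with the unknown *g*. The documents do not support saying that any particular ontamalimab excess would be an artefact, only that the planned tables could not separate the two. It should be corrected because the correction is cheap.

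**What to change.** 1. In SAP 7.1, define an on-treatment window from the first SHP647-303 dose through the Week 52/ET (EOT) visit date and before any SHP647-304 dose, identical in all arms. State the boundary day, since SAP 16.5 starts follow-up on the EOT date and Tables 6 and 9 start it the day after.
2. Use that window for the between-arm TEAE, SAE and AESI comparison and for laboratory and vital-sign PCI counts (SAP 7.2, 7.4, 12.5). SAP 16.5 already cuts rescue exposure at EOT, and SAP 5.5 already excludes medication started after the first SHP647-304 dose. ECG needs no change.
3. Keep the protocol-defined TEAE tables as the overall display, labelled as including follow-up, so that late and possibly drug-related events remain in view.
4. Tabulate events and PCI values after EOT separately, with subjects who entered follow-up as the denominator.
5. Reconcile Protocol 6.2.4 with the synopsis, 3.1, 3.1.3 and SAP 3.3 on who may roll over, and record the analysis change in SAP 14.

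The cost is SAP wording, one derived flag and one extra set of tables, with no new data and no change to patient care. The downside is that late-onset events fall outside the between-arm comparison, though they are still reported. The cut is also not perfectly equal in exposure, because the interval from last dose to the early termination visit can vary.
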